## **7.10. Disease Assessment by CT/MRI**

Baseline evaluation of disease status by CT or MRI within 28 days prior to initiating first treatment on Cycle 1, Day 1. Baseline and subsequent scans to include imaging of the chest, abdomen and pelvis.

Re-scanning to occur every 8 weeks ( $\pm$  7 days) after initiating study treatment on Cycle 1, Day 1.

The  $\pm$  7 day scan window is intended to facilitate flexibility in scheduling re-scans during Week 4 of each EVEN cycle (i.e. Cycles 2, 4, 6, etc.), prior to scheduled infusion of panitumumab / irinotecan on Day 1 of every new ODD cycle (i.e. Cycles 3, 5, 7, etc.).

Scanning on the same day as infusion with panitumumab/irinotecan is allowed, provided scan results receive appropriate RECIST review prior to initiating panitumumab/irinotecan in a new cycle of study treatment (e.g. first re-scan is discouraged, but permitted on Cycle 3, Day 1, prior to panitumumab/irinotecan infusion later that same day).

Additional disease evaluations or increased scan frequency may be performed according to the medical judgment of the patient's study physician.

At End-of-Treatment, CT/MRI required only if the previous CT/MRI was done > 28 days before. At the 28-day Follow-Up visit, CT/MRI scan required only if disease progression not already documented by CT/MRI done at or before the prior EOT visit.

If a patient discontinues the study for reason other than progressive disease confirmed by CT or MRI (e.g. adverse event), then CT or MRI scans of the chest, abdomen and must be continued every 8 weeks ( $\pm$  7 days) until disease progression is confirmed for up to 1 year.

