A similar linear regression will be conducted to predict change in tumor size by the change in PET  $SUV_{max}$  measured just prior to cycle 2. Using a standard deviation of 2 from table 11, we can estimate the SD of the difference in PET  $SUV_{max}$  as  $\sqrt{2V(1-r)}$  where  $V$  is the assumed common variance (for a single SD of 2, the  $V=4$ ) of the two measurements and  $r$  is the correlation between them. For a correlation set of 0.3, 0.5, and 0.7, the SD's of the difference in PET  $SUV_{max}$  are 2.36, 2, and 1.54. The data in table 12 reflect an average (SD) correlation between change in tumor size and  $\Delta SUV_{max}$  of  $0.475 \pm 0.0003$ .

Table 13. True slope estimates required to achieve 80% power to reject the null hypothesis of no association between change in PET $SUV_{max}$ just prior to cycle 2 and change in the sum of index lesions.			
SD for $^{18}F$ -FSPG $SUV_{max}$	SD for Change in Tumor Size at Best Response		
	12	16	24
1.54	3.70	4.93	7.4
2	2.85	3.80	5.70
2.37	2.40	3.21	4.81

Time-to-event. We expect median progression-free and overall survival of approximately 1.9 and 6.4 months, respectively. Power to reject a  $HR=1$  for a single predictor in the Cox regression model depends on the number of events (progressions or deaths), the variability of the predictor, and the true HR [14]. Assuming exponential survival, we estimate that 29 and 21 patients will have progressed or expired by 12 months among the 29 patients in the phase I/II trial. We will use Cox proportional hazards model to estimate the association between PET  $SUV_{max}$  and PFS and OS. Preliminary data suggest  $^{18}F$ -FSPG  $SUV_{max}$  has a standard deviation of 2.04 (95% CI 1.42 to 3.58). Figure 4 illustrates the hazard ratios necessary to reject the null hypothesis that  $HR=1$  versus the alternative that the  $HR \neq 1$  assuming SD estimates for PET  $SUV_{max}$ , a type I error of 5% and 80% or 90% power. For PFS and OS, we expect to have at least 90% power to reject the null hypothesis that the  $HR=1$  if the for a SD PET  $SUV_{max}$  of 1.54 and the true hazard ratios are 1.65 and 1.53 or larger, respectively.

**Figure 5:** True hazard ratios (HRs) scenarios necessary to reject ( $p<0.05$ ) a null hypothesis with 80% and 90% power.

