### Power Analysis:

PFS/OS. Estimated median PFS and OS in this patient population is 1.9 and 6.4 months, respectively, with an estimated 29 and 21 patients progressing or expired by 12 months. In preliminary data, the average standard deviation (SD) and bootstrapped (1000 replications) 95% confidence intervals of the SD for the deltaCt values of 84 genes was 2 cycles (1.85 to 2.14 cycles). Twenty-nine patients provide at least 90% power to reject the null hypothesis that the HR=1, assuming the qRT-PCR SD is 2 for true hazard ratios are 1.35 and 1.42 or larger, respectively.

**Figure 6:** True hazard ratios (HRs) scenarios necessary to reject ( $p<0.05$ ) a null hypothesis with 80% and 90% power.

Change in Tumor Size. Among 20 patients treated with mAb therapy, the mean SD of the change in the sum of index lesions was 6 mm (15.8 mm). Using the SD and their 95% confidence intervals for qRT-PCR (predictor; data provided above) and change in tumor size among 29 patients, table 2 lists the true slope estimates that provide 80% power to reject the null hypothesis of no association between qRT-PCR and tumor response. Given our preliminary data, 29 patients provide 80% power to detect ( $p<0.05$ ) a 3.8 mm change in tumor volume per deltaCt cycle.

Table 14. True slope estimates (mm/cycle) required to achieve 80% power to reject the null hypothesis of no association between baseline qRT-PCR and change in the sum of index lesions.

SD for qRT-PCR	SD for Change in Tumor Size at Best Response		
	12	16	24
1.85	3.08	4.11	6.16

2	2.85	3.80	5.70
2.14	2.66	3.55	5.33

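### The 90% power stated for the gene-expression predictors of PFS and OS is a large-sample figure; the planned Cox test on 29 patients gives about 75% for PFS and about 82% for OS

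*Combined protocol and SAP*

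**What the plan says.** The power analysis under Gene expression signatures (Section 15) states "Twenty-nine patients provide at least 90% power to reject the null hypothesis that the HR=1". The claim is conditional on a predictor SD of 2 cycles and on hazard ratios of at least 1.35 for PFS and 1.42 for OS. The medians behind it are stated first: "Estimated median PFS and OS in this patient population is 1.9 and 6.4 months, respectively". The 12-month event counts are put at 29 for PFS and 21 for OS. The SD of 2 cycles carries a 95% interval of 1.85 to 2.14.

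The Time-to-event paragraph earlier in Section 15 gives the basis. Power for one Cox predictor is said to depend on the number of events, the spread of the predictor and the true hazard ratio. The event counts come from an exponential model: "Assuming exponential survival, we estimate that 29 and 21 patients will have progressed or expired by 12 months". The setting there is "a type I error of 5% and 80% or 90% power", with a two-sided alternative. The same paragraph claims at least 90% power for PET SUVmax with an SD of 1.54 at hazard ratios of 1.65 (PFS) and 1.53 (OS).

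Section 7.10 sets the timing of progression assessment: "Re-scanning to occur every 8 weeks", with a window of 7 days either way. Section 15 makes no allowance for that schedule and does not say how tied event times will be handled.

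**The concern.** The event-count formula is a large-sample approximation. Here it is applied to 29 patients and a strong continuous predictor: log hazard ratio times SD is 0.300 × 2 = 0.60 for PFS. In that setting the formula can overstate the power of the actual Cox test.

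PFS has a second problem. The scan interval, 56 days or 1.84 months, is almost the same as the expected median of 1.9 months. About half of all progressions would therefore be recorded on the first scan date, whereas the formula assumes distinct, exactly known times.

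Relating the gene signature to clinical outcome is a secondary objective of phase II. If power is 75% rather than 90%, the chance of missing the stated PFS effect is 25% rather than 10%. A null result would then carry less weight than the plan implies.

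**Working it through.** **Inputs.** All from Section 15 unless noted: 29 patients; median PFS 1.9 and OS 6.4 months; exponential times; predictor SD 2; hazard ratios 1.35 and 1.42; two-sided 5%; scans every 56 days (Section 7.10). Not in the documents, so assumed: normally distributed predictor, all 29 patients with usable tissue, no dropout.

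**1. Events by 12 months.** 29 × (1 − 2^(−12/median)):
- PFS: 28.6 (plan: 29).
- OS: 21.1 (plan: 21).

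**2. The plan's power figure.** For a continuous Cox covariate, power = Φ(√D × SD × ln HR − 1.96), with D the number of events:
- PFS: √29 × 2 × ln 1.35 = 3.23; Φ(1.27) = 89.8%.
- OS: √21 × 2 × ln 1.42 = 3.21; Φ(1.25) = 89.5%.

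Exactly 90% needs hazard ratios of 1.351 and 1.424, so the plan's figures are reproduced. A one-sided test would give about 94%, so the plan used a two-sided one. At the lower SD limit of 1.85 the same formula gives 85% (PFS) and 84% (OS).

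**3. Simulated power of the planned Cox test** (1,500 to 4,000 trials per scenario; simulation error about 1 point):

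| Scenario | Power |
|---|---|
| PFS, HR 1.35, exact times | 78-80% |
| PFS, HR 1.35, 8-weekly scan dates, Efron ties | 74-75% |
| PFS, HR 1.35, 8-weekly scan dates, Breslow ties | about 45% |
| OS, HR 1.42, censored at 12 months | about 82% |

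**4. Splitting the PFS loss.** From 90% to about 79% is the small-sample failure of the formula. From about 79% to about 75% is the scan schedule, a further 4 to 5 points. The share tied at the first scan is 1 − 2^(−1.84/1.9) = 49%. On scan dates the mean estimated log hazard ratio is about 0.28 against a true 0.300, or 1.32 against 1.35 as a hazard ratio.

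**5. Sensitivity of the PFS scan-date figure (Efron).**
- 7-day scan window added: 74%.
- 15-30% of events dated exactly, as deaths: 74%.
- Sample SD held at exactly 2: 76%.

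Type I error was 4.5%, so the loss does not come from a faulty test. With Breslow ties it was 0.8%, so that test is very conservative.

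**6. Hazard ratio for 90% power on scan dates (Efron).** About 80-81% at 1.40, 87-88% at 1.45 and 90-91% at 1.50.

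**7. SUVmax statements, by the plan's own formula at SD 1.54.**
- PFS, HR 1.65, 29 events: √29 × 1.54 × ln 1.65 = 4.15; power 98.6%.
- OS, HR 1.53, 21 events: √21 × 1.54 × ln 1.53 = 3.00; power 85.1%.

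The OS claim of at least 90% fails before any small-sample loss. The two hazard ratios fit 90% if they are exchanged and used with SD 1.42 (90.2% for PFS, 90.3% for OS). That is one possible explanation; the documents do not state it.

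**The case against.** The best defence is that the plan used a conventional approximation, disclosed what drives it and computed it correctly. That stands: a reader might infer an arithmetic error, and step 2 shows there is none. The objection does not show that the planned test has 90% power.

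The replacement figures also rest on assumptions. With the sample SD held at exactly 2, power is 83% for PFS with exact times and 84% for OS. Survival follow-up runs up to a year after the last dose (Section 6.11), so it can pass 12 months from the start of treatment; at 18 months OS power is about 85%. These points justify listing the assumptions, but none restores 90%.

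A reader might infer that the 8-weekly scans are the main cause. They are not: about 10 of the roughly 15 lost points arise with exact times, and the pull towards no effect is small beside the sampling error from 29 events.

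A reader might also infer that a grouped-time complementary log-log model would recover the loss, since it shows raw power of about 80-83%. Its type I error at this sample size is about 7% (7.2% over 6,000 null runs, 6.9% over 2,700, 7.3% over 1,200), against about 4.7% for Cox with Efron ties. A run of only 400 null trials gave 4.5%, but that is too few to rely on. The model's estimate is also biased away from zero (0.355 against 0.300). With both tests held to a true 5% size, power is 73.7% for the grouped model and 74.0% for Cox, so there is no real gain.

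**Conclusion.** The concern holds as a correction to the stated power. At hazard ratio 1.35 the planned PFS test has about 75% power with Efron ties and 8-weekly scans; at 1.42 the OS test has about 82% at 12 months. The hazard ratio giving about 90% PFS power is about 1.5, not 1.35. These figures assume a normal predictor with SD 2, exponential times, usable tissue from all 29 patients and no dropout; missing tissue or dropout would be expected to lower them.

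Two stronger readings are not supported. The 45% figure is not the plan's power: no ties method is named, so it shows only what is at stake in that choice. And nothing here touches the two-stage response-rate design, because the affected analyses are secondary and no decision rule depends on them.

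**What to change.** In the gene-expression power analysis, restate PFS power at hazard ratio 1.35 as about 75%, or give about 1.5 as the hazard ratio for about 90% power. Restate OS power at 1.42 as about 82%. List the assumptions beside the figures: simulation of the Cox test, normal predictor with SD 2, exponential times, 12 months, all 29 patients usable, no dropout, progression dated at 8-weekly scans.

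Specify Efron ties, not Breslow, for the PFS Cox model. Keep the Cox model as the analysis and do not move to the complementary log-log grouped-time model.

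Recompute the SUVmax statements in the Time-to-event paragraph by the same simulation, after checking which hazard ratio and SD belong to PFS and which to OS.

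The cost is SAP wording and a less favourable stated power for secondary analyses. No patients, scans or samples are added.

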### Exosomal endpoints

Circulating exosomes will be isolated from whole blood samples to explore the potential role of vesicle trafficking in mediating response and resistance to the investigational therapy.

Whole blood is drawn into buffered citrate tubes. For port draws, first draw tubes should be discarded as per standard clinical practice and can be tubes of any kind. The tubes and blood should be kept at ambient/room temperature until processing which should within two hours of blood draw. The whole blood is spun in a centrifuge for 20 min at  $3,000 \times g$  at room

temperature. The resulting crude plasma is aspirated from the top to a new tube. The crude plasma is spun again for 20 min at  $3,000 \times g$  to pellet any remaining platelets. The final plasma preparation is carefully aspirated off into new tubes. The plasma will then be used immediately for exosome isolation or stored at  $-80^{\circ}\text{C}$  for future analysis.

To isolate exosomes, plasma is diluted 10-20 fold with ice-cold phosphate buffered saline (PBS) and centrifuged for 30 min at  $15,000 \times g$ ,  $4^{\circ}\text{C}$ , to pellet and remove larger, non-exosomal extracellular vesicles. The resulting supernatant is passed through a  $0.22 \mu\text{m}$  PES membrane filter to remove any contaminating larger vesicles that might remain. To pellet exosomes, the supernatant is centrifuged at  $120,000 \times g$ ,  $4^{\circ}\text{C}$ . The resulting crude plasma exosome pellet is re-suspended in ice-cold PBS and washed by centrifugation at  $120,000 \times g$ ,  $4^{\circ}\text{C}$ . This wash and centrifugation step is repeated one more time to improve removal of non-exosomal particles and proteins. The final exosome pellet is processed immediately or stored for future use.

Whole blood samples will be collected at three time points during the study for all 29 patients enrolled in phase II: baseline, after cycle 1, and at the end of study/treatment. Expression levels of total EGFR, activated EGFR, and total amphiregulin (AREG), along with the proportion of exosomes containing total EGFR (percent positive EGFR/CD9), exosomes that have active EGFR (percent positive active EGFR/CD9), and exosomes carrying AREG (percent positive AREG/CD9) will be measured at each time point.

Exosomal endpoints are focused on estimation; thus, no formal hypothesis testing will be performed. All point estimates of outcome measures will be accompanied by 95% (e.g. based on standard Gaussian methods or bootstrap methods, as appropriate) confidence intervals. Categorical variables will be summarized in frequency tables. Continuous variables will be summarized using the minimum, 25th, 50th, and 75th percentiles and the maximum value.

## **APPENDIX 1**

### ***Cockcroft-Gault Formula***

*The following formula may be used for estimated creatinine clearance rate (eCCR) using Cockcroft-Gault formula. The use of on-line calculators or formulas which are institution standards for eCCR and differ slightly may also be used. The calculations and results must be filed in the patient's chart.*

When serum creatinine is measured in mg/dL;

$$eC_{CR} = \frac{(140 - \text{Age}) \cdot \text{Mass (in kilograms)} \cdot [0.85 \text{ if Female}]}{72 \cdot \text{Serum Creatinine (in mg/dL)}}$$

When serum creatinine is measured in  $\mu\text{mol/L}$ ;

$$eC_{CR} = \frac{(140 - \text{Age}) \cdot \text{Mass (in kilograms)} \cdot \text{Constant}}{\text{Serum Creatinine (in } \mu\text{mol/L)}}$$

Where Constant is 1.23 for men and 1.04 for women.

**APPENDIX 2**  
***ECOG Performance Status***

Grade	ECOG Performance Status
0	Fully active, able to carry on all pre-disease performance without restriction
1	Restricted in physically strenuous activity but ambulatory and able to carry out work of a light or sedentary nature, e.g., light house work, office work
2	Ambulatory and capable of all self-care but unable to carry out any work activities, Up and about more than 50% of waking hours
3	Capable of only limited self-care, confined to bed or chair more than 50% of waking hours
4	Completely disabled, Cannot carry on any self-care Totally confined to bed or chair
5	Dead

## **APPENDIX 3**

### ***Response Evaluation Criteria In Solid Tumors (RECIST v1.1)***

#### **Measurability of tumor at baseline**

##### **Definitions**

At baseline, tumor lesions/lymph nodes will be categorized measurable or non-measurable as follows:

##### **Measurable:**

Tumor lesions: Must be accurately measured in at least one dimension (longest diameter in the plane of measurement is to be recorded) with a minimum size of:

- 10 mm by CT scan (CT scan slice thickness no greater than 5 mm)
- 10 mm caliper measurement by clinical exam (lesions which cannot be accurately measured with calipers should be recorded as non-measurable)
- 20 mm by chest X-ray

Malignant lymph nodes: To be considered pathologically enlarged *and* measurable, a lymph node must be  $\geq 15$  mm in short axis when assessed by CT scan (CT scan slice thickness recommended to be no greater than 5 mm). At baseline and in follow-up, only the short axis will be measured and followed. See also notes below on “Baseline documentation of target and non-target lesions” for information on lymph node measurement.

##### **Non-measurable:**

All other lesions, including small lesions (longest diameter  $< 10$  mm or pathological lymph nodes with 10 to  $< 15$  mm short axis) as well as truly non-measurable lesions. Lesions considered truly non-measurable include: leptomeningeal disease, ascites, pleural or pericardial effusion, inflammatory breast disease, lymphangitic involvement of skin or lung, abdominal masses/abdominal organomegaly identified by physical exam that is not measurable by reproducible imaging techniques.

##### **Special considerations regarding lesion measurability:**

Bone lesions, cystic lesions, and lesions previously treated with local therapy require particular comment:

##### **Bone lesions**

- Bone scan, PET scan or plain films are not considered adequate imaging techniques to measure bone lesions. However, these techniques can be used to confirm the presence or disappearance of bone lesions
- Lytic bone lesions or mixed lytic-blastic lesions, with identifiable soft tissue components, that can be evaluated by cross sectional imaging techniques such as CT or MRI can be considered as measurable lesions if the soft tissue component meets the definition of measurability described above
- Blastic bone lesions are non-measurable

##### **Cystic lesions**

- Lesions that meet the criteria for radiographically defined simple cysts should not be considered as malignant lesions (neither measurable nor non-measurable) since they are, by definition, simple cysts
- “Cystic lesions” thought to represent cystic metastases can be considered as measurable lesions, if they meet the definition of measurability described above. However, if non-cystic lesions are present in the same patient, these are preferred for selection as target lesions

#### Lesions with prior local treatment

- Tumor lesions situated in a previously irradiated area, or other loco-regional therapy, are usually not considered measurable unless there has been demonstrated progression in the lesion. Study protocols should detail the conditions under which such lesions would be considered measurable

#### Specifications by methods of measurements

##### Measurement of lesions

All measurements should be recorded in metric notation, using calipers if clinically assessed. All baseline evaluations should be performed as close as possible to the treatment start and never more than 4 weeks before the beginning of the treatment.

##### Method of assessment

The same method of assessment and the same technique should be used to characterize each identified and reported lesion at baseline and during follow-up. Imaging based evaluation should always be done rather than clinical examination unless the lesion(s) being followed cannot be imaged but are assessable by clinical exam.

- Clinical lesions: Clinical lesions will only be considered measurable when they are superficial and  $\geq 10$  mm diameter as assessed using calipers (e.g., skin nodules). For the case of skin lesions, documentation by color photography including a ruler to estimate the size of the lesion is suggested. As noted above, when lesions can be evaluated by both clinical exam and imaging, imaging evaluation should be undertaken since it is more objective and may also be reviewed at the end of the study
- Chest X-ray: Chest CT is preferred over chest X-ray, particularly when progression is an important endpoint, since CT is more sensitive than X-ray, particularly in identifying new lesions. However, lesions on chest X-ray may be considered measurable if they are clearly defined and surrounded by aerated lung
- CT, MRI: CT is the best currently available and reproducible method to measure lesions selected for response assessment. This guideline has defined measurability of lesions on CT scan based on the assumption that CT slice thickness is 5 mm or less. When CT scans have slice thickness greater than 5 mm, the minimum size for a measurable lesion should be twice the slice thickness. MRI is also acceptable in certain situations (e.g., for body scans)
- Ultrasound: Ultrasound is not useful in assessment of lesion size and should not be used as a method of measurement

- Endoscopy, laparoscopy: The utilization of these techniques for objective tumor evaluation is not advised. However, they can be useful to confirm complete pathological response when biopsies are obtained or to determine relapse in trials where recurrence following CR or surgical resection is an endpoint
- Tumor markers: Tumor markers alone cannot be used to assess objective tumor response
- Cytology, histology: These techniques can be used to differentiate between PR and CR in rare cases if required by protocol (for example, residual lesions in tumor types such as germ cell tumors, where known residual benign tumors can remain). When effusions are known to be a potential adverse effect of treatment (e.g., with certain taxane compounds or angiogenesis inhibitors), the cytological confirmation of the neoplastic origin of any effusion that appears or worsens during treatment can be considered if the measurable tumor has met criteria for response or SD in order to differentiate between response (or SD) and progressive disease

